8.2. Setting

The study will enroll patients according to the eligibility criteria in participating countries across Europe. The recruiting centers will be representative of each country involved in terms of care management systems, of size and of practices (at least when performing feasibility).

Any patient who meets the eligibility criteria will be invited to participate in the study with no selection by the investigators. The enrollment visit will be performed at the time of the patients' inclusion, after the patients' acceptation of enrollment in the study.

Data will come from medical records and will be collected in routine clinical practice. The enrollment visit will comprise a first section on patients' eligibility for every patient whatever pool they belong to and a second section depending on the treatment started (SU or AXI) at the inclusion.

For patients enrolled in the study when AXI is started as a 2^{nd} line therapy, a retrospective section will be completed at patients' inclusion, to collect data on SU 1^{st} line treatment.

For patients who start AXI when SU is discontinued during the study, the AXI initiation visit will resume baseline data that need to be updated.

Follow-up will be ensured during visits in the context of usual patients' care management (non-interventional study). No visits will be required by the protocol of the study. As long as the

patients are treated with SU or AXI, every visit to the center will be recorded. In accordance with ESMO guidelines and physicians clinical practice is real life, follow-up visits are approximately expected:

- during SU treatment: every 6 weeks (every cycle) with tumor assessment approximately every 3 months with respect to the clinical practice
- during AXI treatment: every 4 weeks (every cycle) with tumor approximately assessment every 2 months with respect to the clinical practice

[figure not shown]
When patients come off SU treatment (i.e. are not receiving AXI) or come off Axitinib (after receiving the SU-AXI sequence) they will be followed up every 6 months (separate form) for survival until the end of the study.

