8.7.1. Efficacy Analysis

Progression-Free Survival (PFS)

Combined PFS of the SU-AXI sequence is defined as the time from when the patient receives the the first dose with SU in first line, until progression or death due to any cause with AXI in 2nd line, whichever occurs first during the SU-AXI sequence. PFS in patients receiving AXI in 2nd line is defined as the time from when the patient receives the first dose of AXI to the time of progression or death due to any cause, whichever occurs first.

Patients who remain progression free at the end of AXI treatment will be evaluated until death, disease progression or the start of a new anticancer therapy.

For the primary endpoints, PFS will be assessed using the Kaplan-Meier method. This method will be applied to derive, survival curves, median event time and a 95% confidence interval for the median.

Kaplan-Meier estimates will also be provided for sub-group analysis of interest:

- Titrated and non-titrated patients, defined in the following section (titration description section), receiving AXI in 2nd line
- Patients receiving AXI in 2nd line post SU depending on the response to SU in 1rst line.
- Country cohorts where feasible (pool size)
- SU 2nd groups depending on the 2nd line treatment :
 - O SU in 1st line- AXI in 2nd line,
 - o SU in 1st line other TKI in 2nd line (sorafenib, pazopanib)
 - O SU in 1st line / mTOR in 2nd line. (temsirolimus, everolimus)

Potential influences of baseline patient characteristics (eg, age, sex, MSKCC risk group) on the primary PFS will be evaluated by Cox proportional regression method.

Time to Treatment to Failure (TTF) and Time to Strategy Failure (TSF)

TTF for the AXI 2nd line is defined as from when the patient receives the first dose of AXI to the time of AXI discontinuation (date completed by the physician) whatever the reason for discontinuation is and whatever the following therapeutic strategy. In case of death while the patient is still treated with AXI, date of death will be considered as date of discontinuation.

TTF for the SU-AXI sequence is as defined as the time from when the patient receives the first dose with SU in first line to the time of AXI discontinuation (date completed by the physician).

TSF for SU-AXI sequence is defined as the time from when the patient receives the first dose with SU in first line to the time of AXI discontinuation (date completed by the physician) without the time between discontinuation of SU and start of AXI.

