5. LONG TERM FOLLOW-UP FORM

Long term follow-up v Patient no longer t			/YYYY) Patient identifier ᆜᆜ ib						
Eastern Cooperative C	ncology Group	(ECOG) available							
If yes, □ 0	□ 1 □ 2	□ 3 □ 4 □ 5							
Death ? ☐ Yes	□No								
If yes, Date of death/ (DD/MM/YYYY)									
Cause tumor-related other cause									
Please observe the definitions and AE and serious AE reporting as defined in the protocol									
Has the patient receive	ed any treatmer	nt for mRCC since las	t visit?						
☐ Yes ☐ No									
If yes, please u	pdate the follo	wing table :							
Drug name	Starting date	Status	Reason for discontinuation						
	 //_/_//_//////////////////////	□ Ongoing	☐ Progressive disease						
Line : □ 2 □ 3 □ 4	لللل	□ Discontinued	Date :						
□ 5 □ other :	(MM/YYYY)	End date/ (MM/YYYY)	☐ Intolerance						
			□ other						
Best response									
□ CR □ PR □ SD □									
PD 🗆 NA									
		□ Ongoing	□ Progression disease						
	(MM/YYYY)	□ Discontinued	Date :/						
Line : □ 2 □ 3 □ 4	(End date/	□ Intolerance						
□ 5 □ other :		ーコーコ (MM/YYYY)	□ other						
Best response									
□ CR □ PR □ SD □									
PD 🗆 NA									
(new lines can be added		nes are received) (Not A	assessable)						
Occurrence of adverse									
Has the patient experience			□ Yes □ No						
sections are still editable			lready available ; the pre-completed						
The safety requirement a	s described in th	e protocol are reminde	d via a click)						

ADONIS CRF Subject ID:

Please complete this form every 6 months until end of the study

ADONIS CRF Subject ID:

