6 ENDPOINTS AND COVARIATES

6.1 EFFICACY/EFFECTIVENESS ENDPOINT(S)

6.1.1 Primary Endpoints

- Progression Free Survival (PFS) under Axitinib in 2nd line post Sunitinib

The PFS will be defined as the time from when the patient receives the first dose of AXI to the time of progression or death due to any cause, whichever occurs first.

PFS status and PFS time will be calculated as detailed below:

Variable name	Definition
PFS status	Patient will not be censored for the PFS analysis (PFS status = 1) in the following cases:
	 Tumor Assessment showing PD in at least one Axitinib follow-up visit (cf. CRF page 29)
	 Death within 3 months after treatment discontinuation / last Tumor Assessment. Death could be reported whether on Axitinib discontinuation page (cf. CRF page 35) or on Study Discontinuation visit (cf. CRF page 37)
	In all other cases, patient will be censored for the PFS analysis (PFS status $= 0$).
	Note: the following cases should be discussed at time of DRMs:
	- Patients with a PD not documented through a Tumor Assessment
	- Patients with no regular Tumor Assessments (i.e. not every 3/4 months)
PFS time	The time to disease progression will be calculated in months as:
(months)	 (Date of first Tumor Assessment showing PD in at least one Axitinib follow-up visit - Start date of Axitinib + 1) / 30.44, if case n°1 described above is reported
	 (Date of death - Start date of Axitinib + 1) / 30.44, if case n°2 described above is reported
	Else, the time to disease progression will be censored as follows:

Variable name	Definition
	 (Date of Axitinib discontinuation - Start date of Axitinib + 1) / 30.44 if patient discontinued Axitinib for any reason other than PD
	 (Date of last follow-up visit - Start date of Axitinib + 1) / 30.44 if patient is lost to follow-up or still under Axitinib
	Note; this could be adapted if necessary (to be discussed at time of DRMs)
	Note:
	- Start date of Axitinib will be the one reported at time of Axitinib initiation visit (cf. CRF page 25 "Therapy started with Axitinib in 2nd line on")
	- Axitinib discontinuation date will be the Date of progression/intolerability or death reported at time of Axitinib discontinuation (cf. CRF page 35)

- Progression Free Survival (PFS) for the sequence Sunitinib-Axitinib

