The PFS will be defined as the time from when the patient receives the first dose of SU in 1st line, until progression or death due to any cause with the 2nd- line treatment considered in the analysis, whichever occurs first.

PFS status and PFS time will be calculated as detailed below:

Variable name	Definition
PFS status	Patient will not be censored for the PFS analysis (PFS status = 1) in the following cases:
	1) Tumor Assessment showing PD in at least one Axitinib follow-up visit (cf. CRF page 29)
	 Death within 3 months after treatment discontinuation / last Tumor Assessment. Death could be reported whether on Axitinib discontinuation page (cf. CRF page 35) or on Study Discontinuation visit (cf. CRF page 37)
	In all other cases, patient will be censored for the PFS analysis (PFS status $= 0$).
	Note: the following cases should be discussed at time of DRMs:

PFIZER CONFIDENTIAL

Page 10 of 41

Variable name	Definition
	- Patients with a PD not documented through a Tumor Assessment
	- Patients with no regular Tumor Assessments (i.e. not every 3/4 months)
PFS time	The time to disease progression will be calculated in months as:
(months)	 (Date of first Tumor Assessment showing PD in at least one Axitinib follow-up visit - Start date of Sunitinib + 1) / 30.44, if case n°1 described above is reported
	 (Date of death - Start date of Sunitinib + 1) / 30.44, if case n°2 described above is reported
	Else, the time to disease progression will be censored as follows:
	 (Date of Axitinib discontinuation - Start date of Sunitinib + 1) / 30.44 if patient discontinued Axitinib for any reason other than PD
	• (Date of last follow-up visit - Start date of Sunitinib + 1) / 30.44 if patient is lost to follow-up or still under Axitinib
	Note; this could be adapted if necessary (to be discussed at time of DRMs)
	Note:
	- Start date of Sunitinib will be the one reported :
	- at time of Sunitinib initiation visit for patients enrolled at SU initiation (cf. CRF page 11 "Therapy started with Sunitinib in 1st line on")
	- at time of Axitinib initiation visit for patients enrolled at AXI initiation (cf. CRF page 26 "Therapy started with Sunitinib in 1st line on")
	- Axitinib discontinuation date will be the Date of progression/intolerability or death reported at time of Axitinib discontinuation (cf. CRF page 35)

- Time to Treatment Failure (TTF) under Axitinib in 2nd line post Sunitinib

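### The SAP's PFS derivation is not the protocol's PFS: after a stop of axitinib without progression it drops later progression, keeps only deaths within 3 months, and otherwise censors back to the stop date

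*SAP*

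**What the plan says.** **Protocol.** Section 8.7.1 defines both PFS endpoints and then sets a rule for those "who remain progression free at the end of AXI treatment will be evaluated until death, disease progression or the start of a new anticancer therapy". Section 8.2 describes follow-up after axitinib: "they will be followed up every 6 months (separate form) for survival until the end of the study".

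**SAP 6.1.1, PFS under axitinib.** The headline definition repeats the protocol: progression or death from any cause. The derivation table is narrower.

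- Progression event: "Tumor Assessment showing PD in at least one Axitinib follow-up visit".
- Death event: "Death within 3 months after treatment discontinuation / last Tumor Assessment", dated at death, with CRF pages 35 and 37 named as sources.
- Censoring after a stop: "Date of Axitinib discontinuation - Start date of Axitinib + 1) / 30.44 if patient discontinued Axitinib for any reason other than PD".

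**SAP 6.1.1, combined PFS.** The same rules apply with the clock starting at sunitinib: "Date of Axitinib discontinuation - Start date of Sunitinib + 1) / 30.44 if patient discontinued Axitinib for any reason other than PD".

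Both tables add that "this could be adapted if necessary (to be discussed at time of DRMs", with no criterion.

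**CRF (protocol Annex 1).** The study plan (1.2) ticks tumour response at long-term follow-up. The long-term form ("Please complete this form every 6 months until end of the study") records best response and progression only against each drug received, so a patient on no new drug has no clear field for progression.

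**The concern.** A patient who stops axitinib for intolerance and progresses later has a PFS event under the protocol and none under the SAP. The two documents therefore define different primary endpoints under one name.

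The 3-month death clause adds a second problem. After a non-PD stop, a patient who dies within the window stays in as an event at the date of death. A patient who survives the window is censored back at the stop date, and the time survived after the stop is discarded. Kaplan-Meier estimation assumes that censoring is unrelated to the later outcome; here the later outcome decides who is censored.

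At stake is what the reported median means. As derived, it is neither the protocol's PFS nor a clean on-treatment PFS. TTF, the other primary endpoint, already counts a stop for intolerability as an event, so PFS is where progression or death after the stop should appear.

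**Working it through.** **1. The rules side by side.** Take hypothetical patients who stop axitinib for intolerance at month 4, with the last tumour assessment also at month 4.

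| After the stop | Protocol 8.7.1 | SAP 6.1.1 |
|---|---|---|
| Progression at month 5, no new drug, alive | Event at 5 | Censored at 4 |
| Death at month 6, no new drug, no earlier progression | Event at 6 | Event at 6 |
| Death at month 8, no new drug, no earlier progression | Event at 8 | Censored at 4 |
| New drug at month 5, death at month 6 | Evaluation ends at 5 | Event at 6 |

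The rules agree in only one of the four cases.

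**2. Is the change authorised?** Protocol 8.7 lets the SAP modify the plan but requires a protocol amendment for major changes to primary endpoint definitions or their analysis. Protocol section 4 lists three amendments, all administrative, and none describes a PFS change.

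**3. The plan's own precision figure.** Protocol 8.5 assumes no censoring before the median. 1.96 × √(0.25/350) = 0.0524, which reproduces the stated 5.2%. If a share p stops first for a non-PD reason and is censored there (exponential times, 3-month death clause left out), Greenwood's variance is multiplied by (1 − p)(2^(1/(1−p)) − 1):

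- p = 0.1: factor 1.044, half-width 0.0524 × √1.044 = 5.35%
- p = 0.2: factor 1.103, half-width 5.50%
- p = 0.3: factor 1.184, half-width 5.70%

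The loss of precision is small. The main issue is what is being estimated.

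**4. Size of the difference in medians.** From the documents: 6.5 months, the investigator-assessed reference in protocol 8.5, used here as the on-drug median. This gives λ = ln 2/6.5 = 0.1066 per month. Assumed, because the documents give no figures:

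- 10, 20 or 30% stop first for a non-PD reason (35, 70 or 105 of 350), with stop hazard λp/(1 − p);
- progression hazard after the stop 0.5 to 3 times λ;
- median survival after the stop 12 months.

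Medians from 1,000,000 simulated patients per cell, first with nobody starting a new drug (protocol rule / SAP rule, months):

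| Post-stop hazard | 10% stop | 20% stop | 30% stop |
|---|---|---|---|
| ×0.5 | 6.48 / 6.41 | 6.48 / 6.31 | 6.46 / 6.16 |
| ×1 | 6.38 / 6.41 | 6.25 / 6.29 | 6.11 / 6.17 |
| ×2 | 6.25 / 6.42 | 5.98 / 6.32 | 5.67 / 6.14 |
| ×3 | 6.16 / 6.42 | 5.79 / 6.30 | 5.43 / 6.18 |

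The SAP median does not depend on the post-stop progression hazard; its small variation down each column is simulation noise. SAP minus protocol runs from 6.16 − 6.46 = −0.30 to 6.18 − 5.43 = +0.75 month.

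**5. Adding the protocol's cut-off at new therapy.** Assume 50% or 80% of stoppers would start a new drug, at a median of 1 month after the stop. SAP minus protocol becomes:

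- 10% stop, ×2: +0.10 or +0.05
- 20% stop, ×2: +0.20 or +0.11
- 30% stop, ×2: +0.31 or +0.17
- 30% stop, ×3: +0.53 or +0.38
- equal hazard: within about 0.1 either way
- 30% stop, ×0.5: about −0.3

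**6. Scale.** An exponential curve with median 6.5 falls at 0.5 × 0.693/6.5 = 0.0533 per month at the median. The planned 5.2% therefore corresponds to about 0.0524/0.0533 ≈ 1.0 month either side. A shift of 0.3 to 0.5 month is a third to a half of that half-width.

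**The case against.** Several counter-arguments have force.

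- **PFS observation does not simply end on the stop day.** A reader might infer this from the censoring line alone. Deaths within 3 months still count, and they pull the SAP median down, partly offsetting the lost progressions. The two effects can cancel.
- **The error need not be large.** A gap approaching one month appears only in a model that leaves out both the 3-month death clause and the protocol's cut-off at new therapy. Neither document supports that model.
- **Combined PFS is less clear.** The protocol ties its event to axitinib and to the SU-AXI sequence, which can be read as on-treatment. This stands. The follow-up sentence in 8.7.1 comes straight after both definitions, so the two texts must be reconciled, but the conflict is certain only for axitinib PFS.
- **Comparison with the reference trial.** A reader might infer that setting the result beside the 6.5-month figure would not be like for like. The documents do not give that trial's censoring rule, so this cannot be judged. SAP section 4 also plans no hypothesis test.
- **The objective is descriptive, and TTF captures stops for intolerability.** True, but a descriptive median still needs one definition, and TTF does not show what happens after the stop.
- **The protocol rule also censors at new therapy, which may itself be informative.** True. Alignment removes the contradiction and the outcome-dependent clause, not every source of informative censoring.

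**Conclusion.** The point holds in this form. Followed as written, the SAP yields a primary axitinib PFS that is not the protocol's, with censoring at the stop that depends on the later outcome. The same derivation is applied to combined PFS, where the protocol wording first has to be clarified. No listed amendment covers the change, and the open note on data review would allow the rule to be chosen after the data are seen.

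The documents fix neither the size nor the direction of the error, because they give no stop rate and no post-stop risk. On the stated assumptions, the SAP median differs from the protocol median by about −0.3 to +0.75 month if nobody starts a new drug, by about −0.3 to +0.5 month if 50-80% of stoppers start one soon, and by no more than about 0.1 month at equal hazard. The simulation concerns axitinib PFS only; no figure is claimed for combined PFS.

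**What to change.** Before data review:

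1. Rewrite both SAP PFS tables to follow protocol 8.7.1. A patient who stops axitinib without PD stays at risk; progression or death before a new anticancer therapy is the event. State whether the others are censored at the start of new therapy or at the last assessment, since 8.7.1 does not settle this.
2. Reconcile the combined-PFS definition with the follow-up sentence in 8.7.1.
3. Take deaths from the long-term follow-up form (CRF page 36, which the SAP already uses for OS) as well as pages 35 and 37.
4. Record on the long-term form, from routine records, whether and when progression occurred off axitinib, in line with the study plan's tumour-response tick.
5. Replace the open adaptation note with a fixed rule, and keep the present derivation as a sensitivity analysis.

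If off-treatment progression cannot be collected, amend the protocol and name the endpoint on-treatment PFS.

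Cost: SAP text, one additional analysis, and a small CRF change that must be carried through a multi-country study. Off-treatment progression will be dated less precisely, because imaging follows routine care.

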8.9.3. Patients lost to follow-up

The pragmatic nature of this study (which involves non-intervention on usual patient management practices) complicates the collection of follow-up data and may increase the number of patients lost to follow-up. Electronic monitoring and the final evaluation questionnaire in the CRF should minimize this number of patients as well as the history and the severity of the studied disease.

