	- Patients with a PD not documented through a Tumor Assessment					
	- Patients with no regular Tumor Assessments (i.e. not every 3/4 months)					
PFS time	The time to disease progression will be calculated in months as:					
(months)	 (Date of first Tumor Assessment showing PD in at least one Sunitinib follow-up visit - Start date of Sunitinib + 1) / 30.44, if case n°1 described above is reported 					
	 (Date of death - Start date of Sunitinib + 1) / 30.44, if case n°2 described above is reported 					
	Else, the time to disease progression will be censored as follows:					
	 (Date of Sunitinib discontinuation - Start date of Sunitinib + 1) / 30.44 if patient discontinued Sunitinib for any reason other than PD 					
	• (Date of last follow-up visit - Start date of Sunitinib + 1) / 30.44 if patient is lost to follow-up or still under Sunitinib					
	Note; this could be adapted if necessary (to be discussed at time of DRMs)					
	Note:					
	- Start date of Sunitinib will be the one reported at time of Sunitinib initiation (cf. CRF page 11 " Therapy started with Sunitinib in 1st line on ")					
	- Sunitinib discontinuation date will be the Date of progression/intolerability or death reported at time of Sunitinib discontinuation (cf. CRF page 17)					

Patients included at time of Axitinib initiation (i.e. retrospective group)

Variable name	Definition					
PFS status	Patient will not be censored for the PFS analysis (PFS status = 1) in the following case: Sunitinib discontinued due to progression (cf. CRF page 27)					
	In all other cases, patient will be censored for the PFS analysis (PFS status $= 0$).					
PFS time	The time to disease progression will be calculated in months as:					
(months)	 (Date of progression under Sunitinib - Start date of Sunitinib + 1 / 30.44, if case described above is reported 					
	Else, the time to disease progression will be censored as follows:					
	 (Date of Sunitinib discontinuation - Start date of Sunitinib + 1) / 30.44 					
	Note:					
	- Start date of Sunitinib will be the one reported at time of Axitinib initiation visit (cf. CRF page 26 " Therapy started with Sunitinib in 1st line on ")					
	- Date of progression under Sunitinib will be the one reported on CRF page 27 (Section "Reason for discontinuation of Sunitinib", item "Progression on")					

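### PFS recognises progression only at a scan but censors at a visit or drug-stop date, which can overstate PFS where scanning lapses before follow-up ends

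*SAP*

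**What the plan says.** SAP 6.1.1 defines a PFS event under axitinib in two ways. The first is "Tumor Assessment showing PD in at least one Axitinib follow-up visit". The second is "Death within 3 months after treatment discontinuation / last Tumor Assessment".

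Patients without an event are censored by one of two rules:

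- The discontinuation date is used "if patient discontinued Axitinib for any reason other than PD".
- The last follow-up visit, computed as "Date of last follow-up visit - Start date of Axitinib + 1) / 30.44", is used "if patient is lost to follow-up or still under Axitinib".

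The SU-AXI sequence PFS repeats both rules with the sunitinib start date as origin. SAP 6.1.2 repeats them for first-line PFS in patients enrolled at sunitinib start, where the visit rule applies "if patient is lost to follow-up or still under Sunitinib". In the retrospective group, sunitinib PFS uses the recorded reason for stopping and is not part of this point.

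Two notes qualify the rules. Cases to be discussed at the data review meetings include undocumented progression and "Patients with no regular Tumor Assessments (i.e. not every 3/4 months". A further note says the censoring could be adapted there. Neither note states a criterion.

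Protocol 8.2 expects visits about every 4 weeks and scans about every 2 months on axitinib (6 weeks and 3 months on sunitinib), but requires no visits. Protocol 8.9.3 says the non-interventional design "may increase the number of patients lost to follow-up", and adds that electronic monitoring and a final questionnaire should keep losses down.

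**The concern.** Apart from death, a patient can have a PFS event only when scanned, but collects event-free time at every visit. If visits continue after scanning has stopped, the patient stays in the risk set during time in which progression could not have been recorded. A patient never scanned on axitinib counts as progression-free for as long as visits go on. The same applies between the last scan and a stop for intolerance.

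Two of the four primary endpoints rest on this rule. The study aims to describe real-world PFS, and Protocol 8.5 sets the axitinib result beside an earlier phase III investigator-assessed median of 6.5 months, with 4.9 months as the lower reference. A shift of several tenths of a month or more would matter to that reading.

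**Working it through.** **1. The plan's own precision.** Protocol 8.5 gives an accuracy of 5.2% for n = 350. Check: 1.96 × √(0.25/350) = 0.0524, which agrees. For scale, under exponential PFS with median 6.5 months the survival curve falls at the median by 0.5 × ln 2/6.5 = 0.0533 per month. So 5.2 points is about 0.0524/0.0533 = ±1.0 month. That calculation assumes no censoring before the median.

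**2. Inputs to the simulation.**

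- From the documents: true median 4.8 or 6.5 months (Protocol 6, independent and investigator assessment); visits every 28 days, or 28/30.44 = 0.92 month; scans about every 2 months, taken as 1.84; administrative cut-off uniform between 24 and 24 + 54 = 78 months (Protocol 8.1.1).
- Assumed, because the documents give no figure: exponential progression; random loss of p = 0, 10, 20 or 30% by 6.5 months, at rate −ln(1 − p)/6.5; scan dates jittered by ±0.92 month; scanning that ends 0, 2 or 4 months before a lost patient's last visit. Deaths were not modelled.

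**3. Method.** Progression is dated at the first scan on or after it occurs, provided scanning has not stopped. Otherwise the patient is censored at the last visit (SAP rule) or at the last scan (alternative). Each scenario has 100,000 patients. The reference is the no-loss scan-dated median, which is what the endpoint would give with complete follow-up.

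**4. Results, months.**

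| True median | No-loss scan-dated | Loss | Scan lapse | Last visit | Excess | Last scan | Excess |
|---|---|---|---|---|---|---|---|
| 4.8 | 5.95 | 10% | 0 | 5.95 | 0.00 | 5.89 | −0.06 |
| 4.8 | 5.95 | 10% | 2 | 6.09 | 0.14 | 5.89 | −0.06 |
| 4.8 | 5.95 | 10% | 4 | 6.24 | 0.29 | 5.88 | −0.07 |
| 4.8 | 5.95 | 20% | 0 | 5.95 | 0.00 | 5.82 | −0.13 |
| 4.8 | 5.95 | 20% | 2 | 6.23 | 0.28 | 5.82 | −0.13 |
| 4.8 | 5.95 | 20% | 4 | 6.82 | 0.87 | 5.82 | −0.13 |
| 6.5 | 7.65 | 10% | 0 | 7.65 | 0.00 | 7.55 | −0.10 |
| 6.5 | 7.65 | 10% | 2 | 7.85 | 0.20 | 7.55 | −0.10 |
| 6.5 | 7.65 | 10% | 4 | 8.06 | 0.41 | 7.55 | −0.10 |
| 6.5 | 7.65 | 20% | 0 | 7.65 | 0.00 | 7.43 | −0.22 |
| 6.5 | 7.65 | 20% | 2 | 8.05 | 0.40 | 7.43 | −0.22 |
| 6.5 | 7.65 | 20% | 4 | 8.82 | 1.17 | 7.45 | −0.20 |

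With no loss, the two rules give the same median.

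**5. Sparser scanning** (true median 6.5, 20% loss, 4-month lapse). With 30% of scans missed, the last-visit excess is 9.64 − 8.41 = 1.23. With scans every 3.5 months it is 9.94 − 8.24 = 1.70. With 30% of scans missed and no lapse, last-scan censoring sits 8.41 − 8.06 = 0.35 low.

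**6. Informative loss and early cuts.** A separate simulation assumed a true median of 5.5 months, 1-3% random loss per month and 0-20% of patients lost between progression and the next scan. Last-scan censoring was closer to the scan-dated median in all 26 scenarios with at least 5% informative loss. The two rules differed by 0.04-0.5 month at the final analysis and 0.2-0.6 at an early cut.

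**The case against.** The strongest reply is that last-visit censoring is correct when scanning works as expected. If scans are on schedule to the last visit and loss is random, the patient really was at risk of a scan-dated event until then. The no-lapse rows show this: 7.65 against 7.65. A further independent run at 20% loss gave 7.49 against 7.47, with last-scan censoring at 7.31. So a reader who inferred that the rule always raises PFS would go too far, and last-scan censoring has a small downward bias of its own. This stands.

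Other tempting readings also fail:

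- **Excess over the true median.** Scan dating alone moves 6.5 to 7.65 with no loss at all. That gap is not due to the censoring rule.
- **Patients still on axitinib.** Someone enrolled at axitinib start has at least 24 months of follow-up and is censored far beyond a 4.8-6.5 month median. Only a patient enrolled at sunitinib start who switched late could be on drug with short axitinib follow-up. At the final analysis early losses are what matter.
- **Long unscanned gaps as the norm.** On schedule the simulated mean gap is about 0.9-1.0 month. Longer gaps need lapsed scanning.
- **An error-rate problem.** SAP 4.2 plans no statistical test, so this concerns an estimate, even though Protocol 8.5 describes a powered comparison.

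The SAP also has partial protection. Deaths within 3 months count as events, and irregular scanning and undocumented progression go to data review. But a case marked for discussion without a criterion is not a rule, and deciding a primary-endpoint rule once data are in view is itself a reason to settle it earlier.

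**Conclusion.** The concern holds in conditional form. The SAP ties progression to scans and censoring to visits or stop dates. This can overstate PFS when scanning lapses before the last visit, or when patients drop out between progressing and the next scan. The documents do not show that either will happen, but they require no visits, foresee irregular scanning and acknowledge possible extra losses.

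For the axitinib median at the final analysis, with 10-20% early random loss and scans about every two months, the inflation is 0 (no lapse) to about 1.2 months (20% loss, 4-month lapse). It reaches 1.7 months if scans are every 3.5 months, and informative loss adds to it. The upper end is comparable to the ±1.0 month sampling precision. Loss rates and lapse lengths are assumptions. Leaving out deaths probably overstates the effect somewhat, because the 3-month death rule would capture some hidden progression.

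The sequence PFS and sunitinib PFS share the rule but were not quantified. The annual descriptive analyses (SAP 3) are more exposed, because many patients will still be on drug with short follow-up.

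**What to change.** In SAP 6.1.1 (both PFS endpoints) and SAP 6.1.2 (prospective sunitinib PFS):

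1. In both censoring branches (lost or still on drug, and stopped for a reason other than progression), censor at the last tumour assessment without progression, or at day 1 if there is none after baseline. Changing only the first branch would mix scan-based and other censoring dates.
2. Report the present last-visit and discontinuation-date censoring as a sensitivity analysis. State that the visit meant is an axitinib visit, as the TTF rule already does.
3. Write the missed-scan rule into the SAP before data review, including what counts as an irregular schedule and how progression without a scan is handled.
4. Report the number of patients with no scan after baseline and the distribution of the gap from last scan to last visit, so that readers can judge which scenario applies.
5. Reconcile the discontinuation branch with Protocol 8.7.1, which continues evaluation after axitinib until death, progression or new therapy.

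The cost is SAP wording and one extra Kaplan-Meier run per endpoint. Assessment dates are already on the sunitinib and axitinib follow-up forms. The drawback is that, under purely random loss, last-scan censoring sits roughly 0.05-0.3 month below the no-loss scan-dated median at the final analysis, and up to about 0.6 at an early cut. Day-1 censoring also removes never-scanned patients from the estimate. The sensitivity run shows both effects.
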